9 ASSESSMENT OF SAFETY

9.1 Specification of Safety Parameters

Safety monitoring for this study will focus on unanticipated problems involving risks to participants, including unanticipated problems that meet the definition of a serious adverse event.

9.1.1 Unanticipated Problems

The Office for Human Research Protections (OHRP) considers unanticipated problems involving risks to subjects or others to include, in general, any incident, experience, or outcome that meets **all** of the following criteria:

- unexpected in terms of nature, severity, or frequency given (a) the research procedures that are described in the protocol-related documents, such as the IRB-approved research protocol and informed consent document; and (b) the characteristics of the subject population being studied;
- related or possibly related to participation in the research ("possibly related" means there is a reasonable possibility that the incident, experience, or outcome may have been caused by the procedures involved in the research); and
- suggests that the research places subjects or others at a greater risk of harm (including physical, psychological, economic, or social harm) than was previously known or recognized.

9.1.2 Adverse Events

An adverse event is any untoward or unfavorable medical occurrence in a human subject, including any abnormal sign (for example, abnormal physical exam or laboratory finding), symptom, or disease, temporally associated with the subject's participation in the research, whether or not considered related to the subject's participation in the research.

9.1.3 Serious Adverse Events

A serious adverse event (SAE) is one that meets one or more of the following criteria:

- Results in death
- Is life-threatening (places the subject at immediate risk of death from the event as it occurred)
- Results in inpatient hospitalization or prolongation of existing hospitalization

- Results in a persistent or significant disability or incapacity
- Results in a congenital anomaly or birth defect
- An important medical event that may not result in death, be life threatening, or require hospitalization may be considered an SAE when, based upon appropriate medical judgment, the event may jeopardize the subject and may require medical or surgical intervention to prevent one of the outcomes listed in this definition.

9.2 Time Period and Frequency for Event Assessment and Follow-Up

Unanticipated problems will be recorded in the data collection system throughout the study.

The PI will record all events with start dates occurring any time after informed consent is obtained until 7 (for non-serious AEs) or 30 days (for SAEs) after the last day of study participation. At each study visit, the investigator will inquire about the occurrence of AE/SAEs since the last visit. Events will be followed for outcome information until resolution or stabilization.

9.3 Characteristics of an Adverse Event

9.3.1 Relationship to Study Intervention

To assess relationship of an event to study intervention, the following guidelines are used:

- 1. Related (Possible, Probable, Definite)
 - a. The event is known to occur with the study intervention.
 - b. There is a temporal relationship between the intervention and event onset.
 - c. The event abates when the intervention is discontinued.
 - d. The event reappears upon a re-challenge with the intervention.
- 2. Not Related (Unlikely, Not Related)
 - a. There is no temporal relationship between the intervention and event onset.
 - b. An alternate etiology has been established.

9.3.2 Expectedness of SAEs

The Study PI will be responsible for determining whether an SAE is expected or unexpected. An adverse event will be considered unexpected if the nature, severity, or

frequency of the event is not consistent with the risk information previously described for the intervention.

9.3.3 Severity of Event

The following scale will be used to grade adverse events:

- 1. Mild: no intervention required; no impact on activities of daily living (ADL)
- 2. Moderate: minimal, local, or non-invasive intervention indicated; moderate impact on ADL
- 3. Severe: significant symptoms requiring invasive intervention; subject seeks medical attention, needs major assistance with ADL

9.4 Reporting Procedures

9.4.1 Unanticipated Problem Reporting to IRB and NIDCR

Incidents or events that meet the OHRP criteria for unanticipated problems require the creation and completion of an unanticipated problem report form. OHRP recommends that investigators include the following information when reporting an adverse event, or any other incident, experience, or outcome as an unanticipated problem to the IRB:

- appropriate identifying information for the research protocol, such as the title, investigator's name, and the IRB project number;
- a detailed description of the adverse event, incident, experience, or outcome;
- an explanation of the basis for determining that the adverse event, incident, experience, or outcome represents an unanticipated problem;
- a description of any changes to the protocol or other corrective actions that have been taken or are proposed in response to the unanticipated problem.

To satisfy the requirement for prompt reporting, unanticipated problems will be reported using the following timeline:

- Unanticipated problems that are serious adverse events will be reported to the IRB and to NIDCR within 5 business days of the investigator becoming aware of the event.
- Any other unanticipated problem will be reported to the IRB and to NIDCR within 15 business days of the investigator becoming aware of the problem.
- All unanticipated problems should be reported to appropriate institutional officials (as required by an institution's written reporting procedures), the supporting

agency head (or designee), and OHRP within one month of the IRB's receipt of the report of the problem from the investigator.

All unanticipated problems, including unanticipated problems that are SAEs, will be reported to NIDCR through the Rho Product Safety centralized reporting system :

- Product Safety Fax Line (US): [name]
- Product Safety Fax Line (International): [contact]
- Product Safety Email: [contact]

General questions about SAE reporting can be directed to the Rho Product Safety Help Line (available 8:00AM – 5:00PM Eastern Time):

- US: [name]
- International: [contact]

For any unanticipated problem meeting the SAE criteria, the study clinician will complete a Serious Adverse Event Form and will submit via fax or email within the timelines stated in Section 9.4.1. Once submitted, Rho Product Safety will send a confirmation email to the investigator within 1 business day. The investigator should contact Rho Product Safety if this confirmation is not received. This process applies to both initial and follow-up SAE reports.

10 STUDY OVERSIGHT

In addition to the PI's responsibility for oversight, study oversight will be under the direction of a Data and Safety Monitoring Board (DSMB) composed of members with appropriate clinical, statistical, scientific, and ethical expertise. The NIDCR will appoint the Board. The DSMB will meet annually to assess safety and efficacy data (if applicable), study progress, and data integrity for the study. If concerns arise, more frequent meetings may be held. The DSMB will operate under the rules of an NIDCR-approved charter that will be approved at the organizational meeting of the DSMB. The DSMB will provide recommendations to the NIDCR.

11 CLINICAL SITE MONITORING

Clinical site monitoring is conducted to ensure that the rights of human subjects are protected, that the study is implemented in accordance with the protocol and/or other operating procedures, and that the quality and integrity of study data and data collection methods are maintained. Monitoring for this study will be performed by NIDCR's Clinical Research Operations and Management Support (CROMS) contractor. The monitor will evaluate study processes and documentation based on NIDCR standards and the International Conference on Harmonisation (ICH), E6: Good Clinical Practice guidelines (GCP).

Details of clinical site monitoring will be documented in a Clinical Monitoring Plan (CMP) developed by the CROMS contractor, in collaboration with the NIDCR Office of Clinical Trials and Operations Management (OCTOM) and the NIDCR Program Official/Project Scientist. The CMP will specify the frequency of monitoring, monitoring procedures, the level of clinical site monitoring activities (e.g., the percentage of subject data to be reviewed), and the distribution of monitoring reports. Some monitoring activities may be performed remotely, while others will take place at the study site(s). Staff from the CROMS contractor will conduct monitoring activities and provide reports of the findings and associated action items in accordance with the details described in the CMP. Documentation of monitoring activities and findings will be provided to the site study team, the study PIs, OCTOM, and the NIDCR. The NIDCR reserves the right to conduct independent audits as necessary.

12 STATISTICAL CONSIDERATIONS

12.1 Study Hypotheses

[figure not shown]
The primary hypothesis this study tests is as follows: Participants receiving the oral health CHW intervention will have improved oral health behaviors, as measured using self-reported brushing frequency and observed plaque score, at 12 months compared to participants receiving usual care.

12.2 Sample Size Considerations

Study design: 10 clinics and 10 WICs, cluster randomized allocation to two arms.

Brushing frequency: Brushing frequency is an ordinal variable with three categories: <1 a day, once a day, 2 or more times a day measured at baseline, 6 months, and 12 months. The proportion of responses (from the pilot study) in the reference population is p0 = (0.16, 0.26, 0.58). We assume cross-time correlation due to repeated observations is 0.7, which is a reasonable assumption for behavioral outcomes. We assumed the interclass correlation (ICC) due to clustering in sites is 0.01. (Using CO-OP UH2 pilot

data, the ICC was 0. When 3 sites were added to these data, the ICC was still 0. This may simply reflect a small sample size. Alternatively the ICC due to site clustering may be so small as to be negligible. Therefore, we feel 0.01 is a conservative assumption.) We also assumed the effect size of 2 between arms at the study endpoint expressed as OR. This effect size translates to the following proportion of frequency of brushing in the intervention arm: p1 = (0.09), 0.18, 0.73).

The power calculation used Monte Carlo simulation based on 1000 datasets (see below for details). We used a proportional odds model in the power simulation. To achieve power of 80%, we will need to recruit 21 participants from each cluster (420participants total). The sample size calculation controls for multiplicity of having two outcomes measures by Bonferroni adjustment (Type 1 error = 0.025). The proposed sample size is a conservative estimate as the simulation does not take into account stratification due to clinics and WICs. The analysis will control for outcome imbalance between clinics and WICs via covariate adjustment and hence increase precision of the estimates.

Data Generating Model for Power Simulation

We followed a mixed-effect ordinal logistic model motivated by an underlying latent variable.⁴⁹ The three-level data structure was defined as follows. We assumed that there are $k = 1, ..., n_{ij}$ level-1 units that are nested within $j = 1, ..., n_i$ level-2 units that are, in turn, nested within i = 1, ..., n level-3 units. In the case of our longitudinal cluster-randomized trial, the level-1 observations are the measurement occasions, level-2 corresponds to subjects, and level-3 corresponds to sites. Assuming a logistic response function for outcome with c = 1..., C ordered categories, the three-level mixed effect model for the cumulative probability of a response is given by

$$\log \frac{P_{ijkc}}{\left(1-P_{ijkc}\right)} = \gamma_c - \left(\beta_1 G_i + \beta_2 T_{ijk} + \beta_3 G_i T_{ijk} + \upsilon_{ij} + \upsilon_i\right)$$

To identify the model, we set the intercept to zero and estimated C-1 threshold parameters. Here, $P_{ijkc} = \Pr(Y_{ijk} \le c)$ is the probability of a response falling within the *c* lower categories. With respect to the random effects, it was assumed that the level-2 random intercept (i.e., subject-specific intercept) was normally distributed as $v_{ij} \sim N(0, \sigma_2^2)$ and the level-3 random intercept (i.e., cluster-specific intercept) was $v_i \sim N(0, \sigma_3^2)$. The random components were assumed to be independent from each other. For the fixed effects the parameter β_1 represents the intervention effect at baseline (set up at zero), and the parameter β_2 represents the slope associated with the time effect in the control group. Finally, the intervention-by-time parameter, β_3 , the effect of primary interest, represents the difference in slopes for the outcome between the intervention groups.

Plaque score: Plaque score is described using the Simplified Oral Hygiene Index -Maxillary Incisor (OHI-MIS). Our sample size calculation is based on a statistical calculation of power using an effect size = 0.40 for the two arm comparison at the end of study. Our estimates of baseline OHI-MIS scores from the pilot study (mean=1.2, SD=0.78) suggest this effect size corresponds to a change of 0.31 units between arms. In order to detect this "moderate" effect size, with two-sided Type I error α = 0.025 (Bonferroni correction due to multiplicity) and Power = 0.80, each arm should have 141 participants, for a total of 282. Calculations employed Rochon's 1998 GEE method, as implemented in the SAS GEESIZE v. 3.1 macro implemented by Dahmen, et al.⁵⁰ We assumed 0.7 ICC due to repeated measures. To further account for the clustering effect due to site (ICC=0.01), the minimum needed sample size to recruit is 170 per arm or 340 total.

Both sample calculations assume 15% attrition at each follow-up (6- and 12-months).

12.3 Final Analysis Plan

The primary study objective is to evaluate the efficacy of a one-year oral health CHW intervention, compared to usual care, to improve self-reported brushing frequency and observed plaque index in low income urban children under the age of 3 years old.

Modern best practice for multilevel data is generalized mixed-effect models with random parameters to account for repeated measurements and clustering in sites.⁵⁰⁻⁵² For frequency of brushing, we will employ a random-effect ordinal regression model. The OHI-MIS will be analyzed as continuous outcome using a linear random-effect model. (Although each surface is scored ordinally, the Central Limit Theorem says that a mean - even of 4 within person measures - in a sample size of at least 25 follows the Normal [Gaussian] distribution.⁵³) The model specification that follows pertains to both outcomes. The between-subjects factors - usual care or CHW, within-subjects occasions of measurement -- time, and their interaction will be in the model. The interaction term is the focus of the analysis. We will employ Bonferroni-Holm adjustments to control for multiplicity, which is a sequentially rejective procedure that provides a more powerful test than the Bonferroni correction.⁵⁴ For this, the smallest of the two outcomes p-value will be compared to 0.025, and if rejected the second p-value will be compared to 0.05 to claim significance. Fixed effect indicators for clinic and WIC sites as well as all other variables used in restricted randomization will be included in all models. Guidance specific to cluster-randomized trials will be followed.⁵⁵⁻⁵⁷ The analysis will be carried out under intention-to-treat (ITT) principles, implying that respondents who are randomized must be represented in analysis and therefore have missing data imputed.⁵⁸ We anticipate data missing at random (MAR)⁵⁹, but will be vigilant for data not MAR (NMAR) as well. Imputation methods adapted for cluster-randomized designs will also be employed.60-62

Analysis of the exploratory aim with the hypothesis of no difference between sites will extend models described above with a three-way interaction: time by group by site. The analysis will follow standard mixed model approaches described in Hedeker & Gibbons.⁶³ We will estimate the intervention effect (average change in the outcome) at the last follow up conditional on site type. The 95% confidence interval (CI) of site difference in the estimated means will be compared to a pre-specified acceptance criterion (scientifically justified maximum difference of no clinical significance). If the 95% CI is contained within the acceptance criteria, the equivalence between sites can be declared (based on two one sided tests (TOST) approach).⁶⁴

The cost data will first be summed and presented on the system-level (program costs, separate for clinic and WIC sites). Cost effectiveness can also be determined by combining the mean total cost per participant with change in primary outcomes. We will calculate the incremental cost-effectiveness ratio (ICER) for the CHW home intervention compared to usual care, such that $ICER_t = (C_1 - C_0) / (E_{1t} - E_{0t})$, where *C* is cost and *E* is effectiveness. Subscript 1 denotes CHW home intervention and subscript 0 denotes the comparison condition. *t* denotes the time period: 6 months and 12 months. 95% confidence intervals for the ICERs will be calculated to evaluate the uncertainty in these

results.⁶⁵⁻⁶⁷ One-way and multi-way sensitivity analyses can be conducted for the key parameters to evaluate whether the ICERs are sensitive to plausible changes in their values. The sensitivity analysis is a check on the robustness and will determine the key parameters impacting the ICERs.

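### Optional efficiency gain: a common baseline mean across arms would sharpen the primary 12-month comparison modestly, and the precision remark in section 12.2 needs a clarifying clause

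*Combined protocol and SAP*

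**What the plan says.** Section 12.3 puts arm, time and their interaction in the model, with random effects for repeated measures and site. It adds: "The model specification that follows pertains to both outcomes", and "The interaction term is the focus of the analysis". On covariates: "Fixed effect indicators for clinic and WIC sites as well as all other variables used in restricted randomization will be included in all models". No covariate-by-time term is named for the primary model; site meets time only in the three-way interaction of the exploratory aim. The section does not say whether time is linear or categorical. Under the Holm rule the smaller p-value is compared with 0.025, and "if rejected the second p-value will be compared to 0.05 to claim significance".

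Section 12.2 sizes brushing from a three-level model with a linear time slope, in which the arm coefficient "represents the intervention effect at baseline (set up at zero"). On that basis: "To achieve power of 80%, we will need to recruit 21 participants from each cluster", or 420 in total, at type I error 0.025. It notes that "the simulation does not take into account stratification due to clinics and WICs" and continues: "The analysis will control for outcome imbalance between clinics and WICs via covariate adjustment and hence increase precision of the estimates".

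Section 5.4.1 randomizes each site at about 90% of its enrollment goal, while section 7.2 places the baseline visit before randomization.

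**The concern.** With the baseline arm difference free, the arm-by-time term is in effect a change-from-baseline contrast: the whole chance baseline gap is subtracted. Where baseline precedes allocation, the expected gap is zero. A model that says so subtracts only the part of the gap that predicts the 12-month result, and is more precise.

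Separately, site type and the minimization variables are constant over time within a site. Read as main effects in a random-intercept model, they shift all of a child's visits equally and cancel from arm-by-time. The precision remark in section 12.2 therefore does not describe the term that section 12.3 tests.

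Only efficiency is at stake, and mainly for brushing, the outcome that sets the sample size.

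**Working it through.** **1. The plan's own figures.** Plaque: n per arm = 2(2.2414 + 0.8416)²/0.40² = 118.8, so 119. Allowing for 15% loss, 119/0.85 = 140, against 141 stated. For sites, 141 × (1 + 20 × 0.01) = 169.2, rounded up to the stated 170. Brushing: my calculations give about 84–87% power at 420, not 80%. The time trend, the scale of the odds ratio and the attrition pattern are not given, so this does not show the stated 80% to be wrong.

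**2. Plaque, complete data, by hand.** From section 12.2: 20 sites × 21 children, within-child correlation 0.7, site ICC 0.01. With total variance 1, the site, child and residual parts are 0.01, 0.69 and 0.30.
- Free baseline: variance of the 12-month arm-by-time term = 2 × (2 × 0.30)/210 = 0.005714, SE 0.0756.
- Variance of the arm difference at one visit = 2 × (0.01/10 + 0.99/210) = 0.01143. Covariance between baseline and 12 months = 2 × (0.01/10 + 0.69/210) = 0.00857. Correlation r = 0.75.
- Common baseline: variance = 0.01143 × (1 − 0.75²) = 0.00500, SE 0.0707, a fall of 12.5%.

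**3. Plaque with 15% loss at each follow-up (72% seen at 12 months), generalized least squares.**
- Free-baseline SE is 0.0861 with or without site covariates, and identical over 40 draws of two three-level site covariates plus site type.
- Common-baseline SE is 0.0818 without covariates (variance −9.6%). With covariates kept, the mean fall over the draws is 7.6% (9.9% with complete data). At an assumed ICC of 0.05, with loss and covariates kept, it is 4.5%.
- Power at 0.40 SD and 0.025: 0.40/0.0861 − 2.2414 = 2.41, or 99.2%. Without covariates the common baseline gives 99.6%.

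**4. Brushing.** Expected information for the section 12.2 ordinal model: reference proportions (0.16, 0.26, 0.58), OR 2 read as population-level (conditional log-odds 1.390), the same correlation, ICC and loss. Power = Φ(1.390/SE − z), with z = 2.2414 at 0.025 and 1.960 at 0.05.

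| Model | SE | Power at 0.025 | Power at 0.05 |
|---|---|---|---|
| Free baseline, categorical time, with or without covariates | 0.4153 | 86.5% | 91.7% |
| Free baseline, linear time | 0.4111 | 87.3% | 92.2% |
| Common baseline, categorical time, balanced covariates kept | 0.3900 | 90.7% | 94.6% |
| Common baseline, categorical time, unbalanced covariates kept | 0.3952 | 89.9% | 94.0% |

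Against the categorical free model the variance falls by 1 − (0.3900/0.4153)² = 11.8% or 1 − (0.3952/0.4153)² = 9.4%. Against the linear free model, if that is what section 12.3 intends, it falls by 10.0% or 7.6%. A separate simulation of 800 datasets with linear time went from 84.9% to 88.9% at 0.025 with covariates kept. Its fit ignored the site random effect, so about 3 points is the safer reading.

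**5. What the site-type term sharpens (plaque, with loss).** Suppose clinics and WICs differ by 0.2 or 0.4 SD (assumed), with an omitted site type treated as extra site variance D²/4. Including site type then changes the model-based variance as follows:
- arm-by-time, free baseline: no change;
- 12-month arm difference (arm plus arm-by-time), free baseline: −13% or −38%;
- common-baseline contrast: −1.6% or −4.2%.

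**6. Families enrolled after allocation.** Suppose 10% of CHW-site families differ by 0.5 SD on plaque (assumed). The baseline gap is 0.10 × 0.5 = 0.05 SD, and the common-baseline model subtracts 0.75 × 0.05 = 0.0375.
- If the difference persists: common baseline +0.0125 SD, free baseline 0.
- If it affects baseline only: common baseline −0.0375 SD, free baseline −0.050 SD.

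Excluding these families, the common-baseline SE is 0.403–0.409 for brushing, against 0.412 for the planned model on all families with the same random seed (variance −1.5% to −4.3%). For plaque it is 0.0862 against 0.0861.

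**The case against.** The strongest reply is that nothing is broken. Arm, time and arm-by-time is a standard specification, and a free baseline protects against a persisting gap among late-enrolled families. The gain of a few points is smaller than the uncertainty about the starting power. All of that stands, and it is why this point is optional.

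A reader might infer that the precision remark in section 12.2 is false and props up the sample size. The documents do not support that. The remark concerns the estimates, not arm-by-time specifically. The Protocol Summary describes the primary analysis as a comparison of arms at 12 months, and that difference does gain from the site-type term in the planned model if site types differ. The simulation ignored stratification, so no power figure takes credit for the remark.

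It is also fair that section 12.3 does not rule out covariate-by-time terms or richer random effects, and that it calls for imputation, which these calculations do not model. What survives is narrower: on the natural reading, the tested term gains nothing from the site covariates and would gain from a common baseline.

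**Conclusion.** The point holds as an optional efficiency improvement. With covariates kept, a common baseline lowers the variance of the 12-month contrast by roughly 8–12% for brushing: about 3–4 power points at 0.025 and 2–3 at 0.05, from about 84–87% and 90–92%. For plaque it is about 7–10% at ICC 0.01 and 4–5% at ICC 0.05, with no practical effect on power.

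These sizes assume random intercepts, covariates as main effects, correlation 0.7, 15% loss at each follow-up and OR 2 on the population scale. The intervention-arm proportions in section 12.2 fit that scale: halving the cumulative odds of 0.16 and 0.42 gives 0.087 and 0.266, hence (0.09, 0.18, 0.73). With a t reference on 18 degrees of freedom, brushing power at 0.025 goes from 80.7% to about 85%.

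A reader should not infer that the planned test is biased or invalid, that the trial is undersized, or that the randomization covariates should be dropped.

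**What to change.** In section 12.3, prespecify for both primary outcomes:
- no arm main effect at baseline, categorical time, and arm-by-time at 6 and 12 months;
- the randomization covariates and site random effect kept, stating whether those covariates also interact with time;
- the 12-month arm difference as the primary estimate;
- two sensitivity analyses: the current free-baseline model, and the common-baseline model excluding families whose baseline visit followed their site's allocation.

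In section 12.2, add a clause saying that, if site types differ, site-type main effects sharpen the 12-month arm difference and the common-baseline contrast, but not arm-by-time in the current free-baseline model.

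The cost is SAP wording, two extra analyses and a flag for baseline visits made after allocation. The downside is that equal expected baselines are not guaranteed for the roughly 10% of families who may enroll late. In the example above that means a plaque shift of about 0.01–0.04 SD, and the exclusion analysis that guards against it keeps little of the brushing gain and none of the plaque gain.
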